We will monitor the Grade 3+ toxicity rate over 2 treatment cycles (28 days/cycle). Patients treated on Phase 1b at the MTD will be included for Phase II toxicity monitoring. Assuming 9

patients from phase 1b, the total sample size for toxicity monitoring will be $29+9=38$. Formally, we will stop accrual if at any time: $\text{Pr}(\text{Grade 3+ toxicity} > 0.20 \mid \text{Data}) > 0.90$, with a prior beta(0.1, 0.4). Stopping boundaries given an initial cohort of 6 followed by cohorts of 6 patients and with a total of up to 38 patients are:

Table 22. Safety Stopping Boundaries for Phase II

Number of Total Patients (Cohorts of 6)	Discontinuation of arm if Grade 3+ toxicity \geq
6	3
12	5
18	7
24	8
30	10
38	12

Below shows the operating characteristics of toxicity monitoring rule:

Table 23. Operating Characteristics of Toxicity Monitoring

True Toxicity	Probability of Early Stop	Avg. N Patients*
.1	.02	37.4
.2	.19	33.0
.3	.57	23.9
.4	.89	14.7
.5	.99	9.7

*include assumed 9 patients in phase I

Considering that patients with ER+ breast cancer will receive additional treatment with an aromatase inhibitor, in addition to the above overall toxicity monitoring rule, we will perform additional safety monitoring for the first 3 and 6 patients of ER+ breast cancer patients using the BON de-escalation boundaries provided in Table 18. That is, ≥ 2 out of 3 or 6 ER+ breast cancer patients experience a DLT after receiving additional treatment with an aromatase inhibitor, the enrollment of ER+ breast cancer will be paused and dose reduction may be performed for ER+ breast cancer patients based on the totality of the data.

Analyses of secondary outcomes will occur after all subjects have completed the study or completed at least 3 treatment cycles, each spanning 28 days, for a total of 84 days. A 95% level of confidence will be assumed.

Incidence of adverse events will be summarized by CTCAE level as counts with percentages.

Clinical benefit rate (CBR) is defined as the rate of patients who achieved complete response, partial response and stable disease for ≥ 24 weeks. The CBR proportion will be reported together with 95% confidence interval.

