Duration of response (DOR) is defined as the period from the date of the first occurrence of a CR or PR until the first date that progressive disease or death is documented. Progression-Free survival (PFS) is defined as the time from treatment onset to either disease progression or death from any cause. 2 year overall survival (OS) is defined as the time from treatment onset to death over 2 years. For events that have not occurred by the time of data analysis, times will be censored at the last contact at which the patient was known to be progression-free for DOR and PFS, or the last time the patient was known to be alive for OS. DOR, PFS and OS will be summarized by the Kaplan-Meier method, including estimates of median and mean survival along with 95% CI.

IND Office Safety and Efficacy Stopping Rule Monitoring:

The Investigator is responsible for completing toxicity summary reports and submitting them to the IND office Medical Monitor for review. These should be submitted as follows:

- **Phase 1b Dose-Finding:**

- A toxicity summary will be submitted after the first 3 evaluable patients complete 2 cycles (56 days) of study treatment, and every 3 evaluable patients thereafter, prior to changing dose levels or moving to the study Phase II portion. IND Sponsor approval will be obtained after each submission, prior to enrolling additional subjects.

- **Phase II – Toxicity Monitoring:**

A toxicity summary will be submitted after every 6 evaluable subjects complete 2 cycles (56 days) of study treatment until enrollment is complete. Patients treated at the MTD in the phase I portion will be included for phase II toxicity monitoring evaluation.

- An additional toxicity summary will be submitted for the subjects with ER+ breast cancer treated at the MTD with AI therapy, after the first 3, and first 6 evaluable patients with ER+ breast cancer treated at the MTD with AI therapy complete 2 cycles (56 days) of study treatment. This toxicity summary may include patients with ER+/HER2- breast cancer treated at the MTD in phase 1b and phase 2. If ≥ 2 out of 3 or 6 patients with ER+ breast cancer experience a DLT at the MTD, the MTD may be decreased to a lower dose level and used for patients with ER+ HER2 negative breast cancer in phase 2.

- **Phase II – Efficacy Monitoring:**

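### Table 23's average sample sizes need a stop at 6 total patients, which cannot occur once the 9 Phase Ib patients in its footnote are counted; the look times are not fixed either

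*Combined protocol and SAP*

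**What the plan says.** All of this is in section 13.2, under toxicity monitoring and the IND Office monitoring rules.

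- **Who is counted.** "Patients treated on Phase 1b at the MTD will be included for Phase II toxicity monitoring". With 9 "patients from phase 1b, the total sample size for toxicity monitoring will be" 29 + 9 = 38. The IND Office text repeats it: "Patients treated at the MTD in the phase I portion will be included for phase II toxicity monitoring evaluation".
- **The rule.** "we will stop accrual if at any time" the posterior probability that the Grade 3+ toxicity rate exceeds 0.20 is above 0.90, with a Beta(0.1, 0.4) prior.
- **The looks.** "Stopping boundaries given an initial cohort of 6 followed by cohorts of 6 patients". Table 22 counts total patients and lists 6, 12, 18, 24, 30 and 38, stopping at 3, 5, 7, 8, 10 and 12 or more events. The last step is 8 patients, not 6.
- **Reporting.** The IND Office receives a toxicity summary each time 6 further evaluable subjects finish two cycles.
- **Performance.** At true rates of 10/20/30/40/50%, Table 23 gives early-stop probabilities of .02/.19/.57/.89/.99 and average N of 37.4/33.0/23.9/14.7/9.7. The footnote to average N reads "include assumed 9 patients in phase I".

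**The concern.** If 9 patients are in the count when Phase II opens, the total can never be 6 at a Phase II look. An average of 9.7 that includes those 9 would mean 9.7 − 9 = 0.7 Phase II patients treated, on average, before a regimen with 50% Grade 3+ toxicity is stopped. A schedule with looks every 6 patients is unlikely to do that.

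Table 23 is the plan's only evidence on how the Phase II toxicity rule performs, and average N tells a reader how many new patients would be exposed to an unsafe regimen.

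The timing is also open. The text allows a stop at any point, sets cohorts of 6 starting at a total of 6, and calls for a summary every 6 evaluable subjects without saying whether that count starts before or after the carried-in patients. With 9 carried in, the first look could fall at 9, 12 or 15.

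**Working it through.** **Inputs (section 13.2).** Prior Beta(0.1, 0.4); toxicity limit 0.20; cutoff 0.90; maximum total 38; 9 carried in.

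**Step 1: boundaries.** The boundary at n is the smallest x for which Pr(p > 0.20 | Beta(0.1 + x, 0.4 + n − x)) > 0.90. At n = 6, two events give 0.729 and three give 0.935, so the boundary is 3. At n = 38, 11 events give 0.894 and 12 give 0.947, so the boundary is 12. All six Table 22 boundaries reproduce. The same rule gives 4 at n = 9, and 6, 7, 9 and 10 at n = 15, 21, 27 and 33.

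**Step 2: the plan's own figures.** Let s(n) be the probability of first crossing at look n, by exact binomial recursion. Early stop = Σ s(n). Average N = Σ n·s(n) + 38·(1 − Σ s(n)). A crossing at 38 is not an early stop.

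| True rate | 10% | 20% | 30% | 40% | 50% |
|---|---|---|---|---|---|
| Early stop, stated | .02 | .19 | .57 | .89 | .99 |
| Early stop, looks 6/12/18/24/30 | .019 | .184 | .575 | .891 | .988 |
| Average N, stated | 37.4 | 33.0 | 23.9 | 14.7 | 9.7 |
| Average N, looks 6/12/18/24/30 | 37.4 | 33.2 | 24.0 | 14.9 | 9.7 |
| Probability of stopping at n = 6 | .016 | .099 | .256 | .456 | .656 |

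Table 23 was therefore computed for a first look at 6 total patients, and at 50% toxicity most of its early stopping happens at that look.

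**Step 3: 9 carried in.**

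| Looks | Early stop at 10/20/30/40/50% | Average N at 10/20/30/40/50% | Gap to stated N at 40/50% |
|---|---|---|---|
| 9/15/21/27/33 | .011/.195/.643/.933/.995 | 37.7/33.9/24.6/16.0/11.6 | +1.3/+1.9 |
| 9/12/18/24/30 | .011/.163/.560/.886/.988 | 37.7/34.2/25.2/16.3/11.5 | +1.6/+1.8 |
| 12/18/24/30 | .006/.138/.536/.879/.987 | 37.9/35.2/27.0/18.5/14.0 | +3.8/+4.3 |
| 15/21/27/33 | .005/.164/.620/.928/.995 | 37.9/35.3/27.3/19.7/16.3 | +5.0/+6.6 |
| Every patient from 9 | .018/.247/.714/.959/.998 | 37.5/32.5/22.1/14.0/10.5 | −0.7/+0.8 |

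No row reproduces the whole of Table 23.

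**Step 4: can any carry-over number fit?**

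- *9 or more.* Looking after every patient from the ninth stops at least as early as any other permitted schedule, so 10.5 is the lowest possible average N at 50%. The stated value is 9.7.
- *8 or fewer.* The total cannot exceed 29 + 8 = 37, so 37.4 at 10% cannot be reached.
- *6, maximum 35.* The n = 6 look is usable, but average N is 34.5/30.8/22.7/14.5/9.7 and the first three rows fail.

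Monitoring the 29 Phase II patients alone and adding 9 gives 37.6/34.9/29.1/22.8/18.6, which also fails.

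**Step 5: Phase II exposure at 50% toxicity (average N − 9).** Stated: 9.7 − 9 = 0.7. Every patient from 9: 10.5 − 9 = 1.5. Looks 9/15/21/27/33: 11.6 − 9 = 2.6. Looks from 12: 14.0 − 9 = 5.0. Looks from 15: 16.3 − 9 = 7.3.

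**The case against.** The operative rule is sound. Prior, cutoff and every boundary are right, and no stopping decision uses average N. Table 23 is correct for the looks in Table 22; on this view the fault is one footnote on a descriptive column. That is fair as to seriousness. It does not make the reported averages right for the trial described.

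The 9 is only an assumption, and Phase Ib is reviewed after every 3 evaluable patients, so a review does occur with 6 patients at a dose. That may explain why the n = 6 row exists. But the footnote adopts the 9, and step 4 shows that no other number fits the whole table.

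The timing statements can be partly reconciled by reading the open-ended phrase as introducing the criterion and the cohorts of 6 as its application. What remains undefined is where the count of 6 starts, and that decides whether the first look is at 9, 12 or 15.

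The upper end of the gap comes from looks starting at 15, which skip Table 22's row at 12. This is correct, and is why each gap is tied to a named schedule.

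The recomputed figures treat the 9 as unselected binomial data, although Phase Ib will have kept the dose because few DLTs were seen. In an illustrative extreme (every Grade 3+ event a DLT, dose kept only with 2 or fewer of 9), looks at 9/15/21/27/33 give an average N of about 21.6 at 50%, not 11.6. The caveat stands, but it moves further from 9.7.

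**Conclusion.** The concern holds. Table 23's average N contradicts its footnote, and no carry-over number reconciles the two.

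The size depends on a schedule the plan does not settle. With six-patient looks and 9 carried in, average N at 40–50% toxicity is understated by 1.3 to 6.6 patients. If the rule is really applied after every patient, the stated N is too high at 30% and 40% (22.1 and 14.0, against 23.9 and 14.7) and too low at 50%.

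Early-stop probabilities suffer less. With looks from 12, the largest fall is about 0.05, from .19 to .14 at 20% toxicity.

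These figures assume exactly 9 carried-in patients, with Grade 3+ events following the same binomial rate as in Phase II. Selection on DLT in Phase Ib is not modelled, because the plan gives no Grade 3+ rate with which to do so. The contradiction with the footnote does not depend on the choice of schedule.

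**What to change.** State one look schedule that counts the carried-in patients, replace the open-ended timing phrase with it, and recompute Tables 22 and 23.

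**Preferred schedule.** Look at total n = 9 before Phase II accrual, stopping at 4 or more events. Then look after every 6 Phase II patients, at 15, 21, 27 and 33, stopping at 6, 7, 9 and 10 or more. Keep 12 at n = 38. The look at 9 can use the toxicity summary already required "prior to changing dose levels or moving to the study Phase II portion". If the number carried in is not 9, say that the boundary follows from the same posterior rule at the actual n, for example 3 of 6.

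**Smaller alternative.** Keep Table 22's rows from 12 onward, name 12 as the first look, and restate Table 23 for that schedule.

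**Cost.** A short recalculation and a few lines of text, with no extra patients and no new report. Under the preferred schedule the stated average N rises by 0.3/0.9/0.7/1.3/1.9 patients at 10/20/30/40/50%. Early-stop probability falls at 10% (.011 against .02) and is about equal or higher elsewhere; the rise at 30% is from .57 to .643. The look at 9 would stop the trial before Phase II with probability 0.086 if true toxicity is 20%, and 0.008 if it is 10%. The team should accept that gate knowingly.

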5.0 Study Endpoints

5.1 Primary Endpoints

- **Safety**

The primary safety endpoint is to determine the safety, tolerability, and dose limiting toxicities (DLT) (Phase 1b) of the combination of capmatinib and neratinib, and of neratinib + capmatinib in combination with an aromatase inhibitor in ER+ MBC.

- **Efficacy**

For the Phase 2 portion of the study, the primary efficacy endpoint is overall response rate (ORR), defined as the rate of patients who achieve partial response or complete response as the best response.

All tumor response will be evaluated by RECIST 1.1 and measured by QIAC system, via research collaboration.

5.2 Secondary Endpoint(s):

- **Clinical benefit rate (CBR)**

Defined as the rate of patients who achieved complete response, partial response and stable disease for ≥ 24 weeks as the best response of treatment.

- **Duration of response (DOR)**

DOR is defined as the period measured from the date of the first occurrence of a CR or PR (whichever status is recorded first) until the first date that progressive disease or death is documented. Patients who have not progressed and who have not died by the date of data cutoff for analysis will be censored at the time of last tumor assessment date. If tumor assessments performed after the date of the first occurrence of a CR or PR showed a different response, DOR will be censored at the date of the first occurrence of a CR or PR plus remaining stable response from that time point.

- **Progression free survival (PFS)**

PFS is defined as the time between date of treatment start to the date of documented disease progression or death, whichever occurs first. Data from patients who have not experienced disease progression or death will be censored at the last tumor assessment date known to be free of disease progression. Data from patients with no post-baseline tumor assessment will be censored at the treatment start date plus 1 day.

- **2 year overall survival (OS)**

2 year OS definition: the proportion of patients in the study who are alive 2 years after enrollment on to the study.

5.3 Exploratory Endpoints:

- For exploratory purposes, ORR, CBR, DOR, PFS, and OS will also be analyzed separately for the sub-group of IBC patients and for the sub-group of advanced or metastatic non-IBC breast cancer patients.
- Assess response per molecular subtype, Hormone Receptor positive (ER and/or PR), HER2 negative and Triple Negative Breast Cancer

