13.2 Phase II Single-Arm Toxicity Monitoring and Efficacy Trial

Phase II single-arm trial will be conducted to assess the overall response rate (ORR) for patients treated at the MTD. Only patients with abnormal HER-family and c-Met signaling activity based on CELsignia MP Test results will be included in the efficacy analysis. The target ORR will be 25%, with unacceptable ORR as 5%.

We will monitor the ORR using the Bayesian optimal phase 2 (BOP2) design (Zhou, Lee and Yuan, 2017)²⁸. The assessment window for ORR monitoring is 4 cycles. Specifically, let n

denote the interim sample size and N denote the maximum sample size. Let p_{eff} denote the ORR and define the null hypothesis $H_0: p_{eff} \leq 0.05$, under which the treatment is deemed as unacceptable. We will stop enrolling patients and claim that the treatment is unacceptable if

$$Pr(p_{eff} > 0.05 | data) < \lambda \left(\frac{n}{N} \right)^\alpha,$$

where $\lambda=0.84$ and $\alpha=0.86$ are design parameters optimized to maximize power under the alternative hypothesis $H_1: p_{eff} = 0.25$, (i.e., the probability of correctly claiming that the treatment is acceptable under H_1), while controlling the type I error rate (i.e., the probability of incorrectly claiming that the treatment is acceptable under H_0) at 0.05. This optimization is performed assuming a vague prior Beta(0.05,0.95) for p_{eff} . The above decision rule leads to the following stopping boundaries and yields a statistical power of 0.95 under H_1 :

Table 20. Optimized Stopping Boundaries

# patients treated	Stop if # responses <=
15	0
29	3

Based on Table 20, we perform the interim analysis when the number of enrolled patients reaches 15. When the total number of patients reaches the maximum sample size of 29, we reject the null hypothesis and conclude that the treatment is acceptable if the number of responses is greater than 3; otherwise we conclude that the treatment is unacceptable. The go/no-go criteria in Table 20 are non-binding and final decision will be based on the total evidence of efficacy.

Below are the operating characteristics of the design based on 10000 simulations using the BOP2 web application, which is available at <http://www.trialdesign.org>.

Table 21. Operating Characteristics

Response rate	Early stopping (%)	Claim promising (%)	Sample size
0.05	46.3	5.3	22.5
0.15	8.7	63.9	27.8
0.25	1.3	94.8	28.8
0.35	0.2	99.6	29.0

Toxicity monitoring

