An efficacy summary will be submitted after 15 evaluable subjects complete 4 cycles of study treatment. Final efficacy summary will be submitted when enrollment is complete. Only patients with abnormal HER-family and c-Met

signaling activity based on CELsignia MP Test results will be included in the efficacy analysis.

A copy of each safety summary report should be placed in the Investigator's Regulatory Binder under "Protocol Summary".

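### Section 13.2 lets every secondary outcome be analysed from day 84, before late entrants can be classified for CBR or reach 2 years, and 2-year OS is defined in two different ways

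*Combined protocol and SAP*

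**What the plan says.** On timing, Section 13.2 gives one rule and exempts no endpoint: "Analyses of secondary outcomes will occur after all subjects have completed the study or completed at least 3 treatment cycles, each spanning 28 days", which it totals as 84 days.

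On CBR, Section 5.2 counts CR, PR and "stable disease for ≥ 24 weeks as the best response of treatment". Section 13.2 adds only this on analysis: "The CBR proportion will be reported together with 95% confidence interval".

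On 2-year OS, Section 5.2 defines "the proportion of patients in the study who are alive 2 years after enrollment on to the study". Section 13.2 says instead: "2 year overall survival (OS) is defined as the time from treatment onset to death over 2 years". It then states: "DOR, PFS and OS will be summarized by the Kaplan-Meier method, including estimates of median and mean survival along with 95% CI". It does not name a 24-month estimate.

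Two other timing statements in Section 13.2 matter here. For the primary endpoint, "The assessment window for ORR monitoring is 4 cycles". For Phase II efficacy monitoring, "Final efficacy summary will be submitted when enrollment is complete"; that summary may cover ORR only.

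Section 7.7 collects survival about every 6 months for 2 years after treatment stops. Section 7.8 ties the end of study to the last data point needed, and names OS. Neither sets an analysis date for CBR or 2-year OS.

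**The concern.** The earliest permitted cut is too short for two of the endpoints it governs. DOR, PFS and OS are censored under Kaplan-Meier and remain estimable with short follow-up. CBR does not have that protection. Patients with CR, PR, progression or death can be classified at once, but a late entrant in ongoing stable disease is neither a success nor a failure. Counting such patients as non-benefit understates CBR, and dropping them changes the denominator. The plan does not say which applies.

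For OS, a 24-month value has no support if nobody in the analysis set has been followed that long. Whatever the cut, the two definitions differ in measure (proportion or time) and in origin (enrollment or treatment onset), so two analysts could report different 2-year OS values from the same data.

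No formal test rests on CBR or OS. However, Section 13.2 makes the go/no-go criteria non-binding and leaves the final decision to the total evidence of efficacy. Secondary results can therefore inform that decision in an open-label, single-arm trial, and the cut date and counting rule should not be left open.

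**Working it through.** **Inputs from the documents.** Minimum time 3 cycles of 28 days (13.2); stable disease for 24 weeks (5.2, 13.2); ORR window 4 cycles (13.2); scans every 2 cycles (7.10, note d); Phase II maximum 29 patients at 0-2 per month per site, one site (4.4, synopsis); screening window 28 days (6.1, item 10).

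**Assumptions.** Even entry, with patient i entering at i/r months (i = 0 to 28, r = patients per month); a month of 30.44 days; treatment start taken as entry; potential follow-up only, with no death or dropout.

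**Step 1: the plan's figure.** 3 × 28 = 84 days reproduces. Against it, 24 × 7 = 168 days for CBR (84/168 = 50%), 4 × 28 = 112 days for ORR, and about 730 days for 2-year OS (84/730 = 11.5%). Scheduled scans fall at days 56, 112 and 168, so a patient at day 84 has had 1 of the 3.

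**Step 2: follow-up at the cut.** With the cut C days after the last entry, the patient k places before the last has C + 30.44k/r days. The table counts patients, out of 29, below 168 days or at 24 months or more.

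| Rate per month | Under 168 days, C = 84 | Under 168 days, C = 112 | At least 24 months, C = 84 | Longest follow-up, C = 84 |
|---|---|---|---|---|
| 2 | 6 | 4 | 0 | 16.8 months |
| 1.5 | 5 | 3 | 0 | 21.4 months |
| 1 | 3 | 2 | 7 | 30.8 months |
| 0.5 | 2 | 1 | 18 | 58.8 months |

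Example at 2/month: 84/15.22 = 5.5, so k = 0 to 5 gives 6 patients. The C = 84 counts under 168 days do not change if the 3-day visit window is added (171 days).

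**Step 3: when nobody reaches 24 months.** 84 days is 2.76 months, and the first entrant has 28/r + 2.76 months. This is below 24 when r > 28/(24 − 2.76) = 1.32 per month, which lies inside the stated 0-2.

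**Step 4: effect on CBR.** Let q be the share of all patients whose benefit is stable disease of at least 24 weeks. The documents give no value; take q = 10-30%. If the late ones are scored as non-benefit, the expected understatement is (number under 168 days) × q/29.

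- C = 84, 1/month: 3 × 0.1/29 = 1.0 to 3 × 0.3/29 = 3.1 points (0.3 to 0.9 patients).
- C = 84, 2/month: 6 × 0.1/29 = 2.1 to 6 × 0.3/29 = 6.2 points (0.6 to 1.8 patients).
- C = 112, 1/month: 0.7 to 2.1 points. C = 112, 2/month: 1.4 to 4.1 points.

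For scale, the exact 95% interval at 10/29 is 17.9% to 54.3%, a half-width of 18.2 points.

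**Step 5: effect of the OS time origin.** The enrollment-to-treatment gap is not stated. Suppose it equals the 28-day screening window, 28/30.44 = 0.92 months, and that OS is exponential, S(t) = 0.5^(t/median). The two definitions then differ by S(23.08) − S(24) = 1.16, 1.36, 1.43 and 1.35 points at medians of 9, 12, 18 and 24 months. Both the gap and the medians are assumptions.

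**The case against.** The strongest reply is that 84 days is a minimum and not a planned cut. The same sentence allows analysis after all subjects complete the study, Section 7.8 names OS as data the study waits for, and neither a 24-week nor a 2-year criterion can be met before its time has elapsed. A sensible analyst would wait. That is a fair account of likely conduct, but it is not what the plan requires: Section 7.8 fixes the end of study rather than an analysis date, and it does nothing for CBR.

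The expected CBR effect is also small beside an 18-point half-width, and it depends on an assumed rate and on one of two possible counting rules. This stands, and it limits the severity. It does not supply the missing rule.

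The count of 0 of 29 covers Phase II only. If Phase Ib patients were included, at the fastest stated rates (cohorts of 3 at months 0, 2, 4 and so on; Phase II from month 12; cut at 12 + 14 + 2.76 = month 28.8), the 9 who entered by month 4 would have 24 months. But Section 13.2 limits the efficacy analysis to patients with abnormal CELsignia results, and that test is an entry criterion for Phase II only, so the Phase II count is the natural one.

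Finally, with complete 2-year follow-up, the Kaplan-Meier value at 24 months equals the simple proportion, leaving only the origin. That is true, but Section 13.2 names the median and mean and not that value, and losses or withdrawals would separate the two.

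**Conclusion.** The concern holds, as something that should be fixed but does not threaten the primary result. The text permits an analysis of CBR and 2-year OS that the data could not support, and it gives no rule for the patients affected.

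At the earliest cut, 2 to 6 of 29 Phase II patients lack 24 weeks of potential follow-up at 0.5 to 2 per month. Only those in ongoing stable disease are unclassifiable. The expected CBR understatement is 1.0-3.1 points at 1/month and 2.1-6.2 points at 2/month, given even accrual, the assumed 10-30% and scoring as non-benefit. Moving the cut to day 112 shrinks the problem without removing it. A 24-month OS value would have no Phase II support above about 1.32 entries per month.

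The conflict between Sections 5.2 and 13.2 on 2-year OS needs no assumption about timing. Its size from the origin alone is about 1.2-1.4 points under the stated gap and medians.

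**What to change.** Replace the 84-day limb in Section 13.2 with a cut for each endpoint.

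- **CBR:** analyse when every patient has at least 24 weeks plus the scan window, or has progressed, died or withdrawn. In any earlier report, state how ongoing stable disease under 24 weeks is counted and how many such patients there are.
- **2-year OS:** analyse 2 years after the last patient enters, as the 24-month Kaplan-Meier estimate with its 95% CI. Use one time origin, worded identically in Sections 5.2 and 13.2 and in the synopsis.

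The cost is wording plus later final reporting: 168 − 84 = 84 days for CBR and 730 − 84 = 646 days for 2-year OS, relative to the earliest cut now allowed. Section 7.7 already plans the survival follow-up, so no new procedures are needed.

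The expected last visit in Section 7.8, 3 years after the first patient, should be checked at the same time. With both phases full at the fastest stated rates, the last entry plus 24 months falls at about month 50 (12 + 14 + 24). The section's later-of clause can accommodate this.

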7.5 Duration of therapy

In the absence of treatment delays due to AEs, the treatment will continue up to 3 years or until disease progression, death of patient for any cause or meeting the treatment discontinuation criteria, whichever comes first.

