7.7 Follow up

Patients will be followed for safety for 30 days following the last dose of study drug, or until receipt of another anticancer therapy, whichever comes first.

Patients who have an ongoing major study treatment related AE upon study completion or at discontinuation from the study will be followed up to 6 weeks until the event has resolved to baseline grade, the event is assessed by the investigator as stable, new anticancer treatment is initiated, the patient is lost to follow-up, the patient withdraws consent, or until it has been determined that study treatment or participation is not the cause of the AE.

After treatment discontinuation, information on survival follow-up and new anti-cancer therapy will be collected via telephone calls, patient medical records, and/or clinic visits approximately every 6 months for 2 years (unless the patient withdraws consent or study is terminated).

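### Kaplan-Meier mean survival is planned for DOR, PFS and OS with no restriction time, so under censoring its value depends on the data cut

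*Combined protocol and SAP*

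**What the plan says.** Section 13.2 summarises DOR, PFS and OS by Kaplan-Meier, "including estimates of median and mean survival along with 95% CI". All three endpoints are right-censored in the same paragraph. For patients without the event, "times will be censored at the last contact at which the patient was known to be progression-free for DOR and PFS", and OS is censored at "the last time the patient was known to be alive for OS". The mean is not described as restricted, no horizon is attached to it, and nothing covers a longest time that is censored.

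Four other statements determine how much follow-up the curves will have:

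- **Section 13.2, timing.** Secondary outcomes may be analysed once all subjects have either completed the study or completed at least three 28-day cycles (84 days).
- **Section 7.5.** "the treatment will continue up to 3 years or until disease progression".
- **Section 7.7.** Survival status is collected after treatment discontinuation, "approximately every 6 months for 2 years (unless the patient withdraws consent or study is terminated").
- **Section 7.8.** The last patient's last visit is expected 3 years after the first enrolment, but the study may end later if OS data arrive later.

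Two-year OS is worded in two ways. Section 5.2 makes it "the proportion of patients in the study who are alive 2 years after enrollment on to the study". Section 13.2 says "2 year overall survival (OS) is defined as the time from treatment onset to death over 2 years".

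**The concern.** The Kaplan-Meier mean is the area under the whole curve. If the largest observed time is censored, the curve stops above zero and the remaining area is unknown. The figure usually reported is then the area up to the largest observed time, which is a restricted mean whose limit was fixed by the accrual pattern and the cut date.

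Reported as mean survival, that figure is too low, and its confidence interval describes a different quantity from the one named. Two cuts of the same trial would give different means with no change in the treatment effect. A later reader comparing the figure with a mean from another study could not tell how much of a difference came from follow-up.

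**Working it through.** **Plan's own figure.** The plan states no figure for any survival endpoint, so there is none to reproduce here. Its only phase II efficacy sizing figure is a power of 0.95 at a response rate of 25% (Table 21: 94.8%). An exact two-stage binomial calculation with the Table 20 boundaries (0/15 and 3/29) gives 94.8%. That rule uses no survival data.

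**Inputs from the documents.** Phase II has at most 29 patients and accrues at most 2 per month (Section 4.4), so accrual takes 29/2 = 14.5 months at the fastest. The earliest analysis comes 84 days after the last entry: 84/30.4 = 2.76 months. Follow-up at that cut therefore runs from 2.76 to 14.5 + 2.76 = 17.26 months.

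**Assumptions.** Event times are exponential with medians of 3 to 18 months, entry is uniform, there is no dropout, and the analysis covers the 29 phase II patients. The true mean is median/ln 2.

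**Result at the 84-day trigger.** The table shows the simulated area under the Kaplan-Meier curve to the largest observed time (4,000 runs).

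| Assumed median | True mean | Average reported mean | Shortfall | Curve still above zero |
|---|---|---|---|---|
| 3 | 4.3 | 4.1 | 0.2/4.3 = 5% | 47% |
| 6 | 8.7 | 7.2 | 1.5/8.7 = 17% | 81% |
| 12 | 17.3 | 10.5 | 6.8/17.3 = 39% | 94% |
| 18 | 26.0 | 12.2 | 13.8/26.0 = 53% | 97% |

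**Effect of moving the cut.** Suppose phase Ib enrols all 18 patients at its fastest rate of 3 per 2 months, which takes 12 months, and phase II follows at 2 per month, ending at month 26.5. A cut at month 36 then gives 9.5 to 24 months of follow-up. At a median of 12 the average reported mean becomes 12.6 months, with the curve above zero in 92% of runs. With the same assumed truth of 17.3, the figure moves from 10.5 to 12.6 because of the cut date alone.

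**Fixed 24-month limit, for comparison.** The restricted mean is true mean × (1 − 2^(−24/median)):

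- median 3: 4.3 × 0.996 = 4.3
- median 6: 8.7 × 0.9375 = 8.1 (unrounded mean 8.66)
- median 12: 17.3 × 0.75 = 13.0
- median 18: 26.0 × 0.603 = 15.7

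**DOR.** At the target response rate about 29 × 0.25 = 7 patients contribute. With 24 months of follow-up each and a median of 6 months, the curve stays above zero in 37% of runs, and the area averages 8.2 against 8.7.

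**The case against.** A reader might infer that censored data from this trial cannot yield a mean at all. The documents do not support that. The Kaplan-Meier mean is defined when the longest time is an event, and with short event times this is common: with 24 months of follow-up for all 29 patients and a median of 3 months, the curve fails to reach zero in only about 10% of runs. Patients have had one to six prior lines in the metastatic setting, so short PFS is plausible.

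A reader might also infer a flat 2 years of follow-up. That misreads Section 7.7, where the 2 years begin at treatment discontinuation. With up to 3 years of treatment, one patient could be followed for 3 + 2 = 5 years. If every patient had 60 months, the curve would stay above zero in 3% of runs at a median of 6 months, 61% at 12 and 95% at 18. The area would average 16.8 against 17.3 at a median of 12, and 23.4 against 26.0 at 18. Long follow-up therefore shrinks the error considerably. It is not assured, because the 84-day condition allows a much earlier cut and the last visit is expected 3 years after the first enrolment. Equally, 84 days is the earliest permitted timing, not a stated intention.

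The phrase about death over 2 years could be read as a 24-month limit on OS. It is not stated as a restriction time, it does not cover PFS or DOR, and it conflicts with the proportion defined in Section 5.2. Even on that reading, the result would need to be labelled a restricted mean.

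Finally, these are secondary, descriptive summaries in a single arm, and the median and a 2-year survival endpoint are already planned. That limits the importance of the point but does not make the unrestricted mean interpretable.

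**Conclusion.** The point holds in a limited form. Followed as written, Section 13.2 can produce a figure called mean survival that is a restricted mean with an unstated, data-dependent limit. At the earliest permitted cut the shortfall is about 0.2 months at a median of 3 months, 1.5 at 6, 6.8 at 12 and 13.8 at 18. For short PFS or DOR this is negligible; for OS with a median of a year or more it is large.

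These sizes rest on assumed exponential medians, because the documents give none, and on the fastest planned accrual with analysis at 84 days. Later analysis reduces them. No decision rule, sample size or safety boundary is affected.

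**What to change.** In Section 13.2, either delete the mean or replace it with restricted mean survival time and a 95% CI, with a horizon stated in advance for each of DOR, PFS and OS. Each horizon must be no longer than the follow-up available at the analysis. A 24-month horizon could not be used at the 84-day trigger after 14.5 months of accrual, when the longest possible follow-up is about 17 months.

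Keep the Kaplan-Meier median with its 95% CI. Report 2-year OS as the 24-month Kaplan-Meier estimate with 95% CI, which brings Section 13.2 into line with the proportion in Section 5.2. Run that analysis only when follow-up reaches 24 months, not at the 84-day trigger.

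The cost is a few lines of text and standard software. No extra patients are needed, and the survival follow-up in Section 7.7 already collects the data. The drawback is a later OS summary: at the fastest accrual, 24 months of follow-up on the last phase II patient is reached 14.5 + 24 = 38.5 months after phase II opens, against about 17 months under the 84-day trigger. Section 7.8 allows for this, because the study may end when the last OS data arrive.
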